8.5.1.1 Sample Analyses

In order to perform safety, pharmacokinetics, immunogenicity,

from approximately 4

mL to 90 mL (this highest volume taken only during the administration visits of Cycle 1) of whole blood volume needs to be collected per visit.

Details on samples collection, handling and shipment will be provided in separate Laboratory Manuals.

Bone marrow morphologic assessment will be performed on bone marrow blood smears.

8.5.2 Assessment of Safety

Safety and tolerability endpoints will be derived from the following measurements/evaluations:

- Incidence, severity, seriousness, and treatment related causality of TESS.
- Frequency of clinically significant changes in:
 - Physical examination and vital signs
 - PS Evaluation
 - Safety laboratory tests
 - 12-lead-ECG.

8.5.2.1 Medical History

Complete medical history will be collected during the Screening Period in order to obtain all the information necessary to confirm the study inclusion and exclusion criteria.

General medical history shall include all the diseases (excluding AML) and conditions, either chronic or not, which are needed to assess the compliance with inclusion/exclusion criteria and those which are relevant according to the Investigator.

The AML specific medical history will include: date of onset of AML, relapsed or refractory status following the last AML treatment, *de novo* or secondary AML status, number and category of previous AML treatments (including auto- and allo-HSCT, if any), duration of the last CR/CRi (relapsed patients), AML karyotype (if available), NPM1 mutational status (if available), FLT3-ITD mutational status (if available), FAB subtype (if available) and previous patient's participation in clinical trials (if any).

General medical history shall be collected starting from 30 days prior to screening.

AML specific medical history shall be collected starting from AML onset date.

8.5.2.2 Physical Examinations and Vital signs

A complete physical examination will be performed at each study visit from Screening to End of Study Visit, except at Visit 5-6, Visit 28-29 and during the End of Treatment period; it includes a general appearance observation and a complete exam of the following body systems/areas: Head, Eyes, Ears, Nose and Throat (HEENT)/Neck, Lymph Nodes, Thyroid, Abdomen, Skin, Cardiovascular, Respiratory, Gastrointestinal, Neurological and Musculoskeletal/Extremities.

Vital signs will be recorded throughout the study at each visit except at Visit 5-6, Visit 28-29/ and during the End of Treatment period. At each study drug administration during Cycle 1, vital signs should be measured prior to study drug administration and following the same time points of blood sampling for safety lab tests (see 14.3). At Cycle 2, they should be measured prior to study drug administration, every 15 minutes during the first hour of study drug administration and 15 minutes after the end of infusion. The following parameters will be measured:

- Heart rate (HR, beats / min)
- Blood pressure (BP, systolic and diastolic, mmHg)
- Breathing rate (BR, breaths / min)
- Body temperature (T, °C).

8.5.2.3 Weight measurement

Body weight (to the nearest 0.1 kilogram [kg] in indoor clothing, but without shoes) will be measured during screening period and at study drug administration visits (during Cycle 1 only prior to the first *"ramp-up"* dose and at Visit 12/Day 15).

8.5.2.4 PS evaluation

Performance Status evaluation will be performed throughout the study at each visit except at Visit 5-6, Visit 28-29 and during End of Treatment period. The ECOG scale will be used.

8.5.2.5 12-Lead ECG

12-Lead ECGs will be performed locally, using standard equipment available at the study sites, during Screening Period and at Visit 1/Day 1, Visit 2/Day 2 and Visit 3/Day 3 (prior to and at the end of the study drug infusion).

Standard 12-Lead ECG will be performed at rest in the supine position. All ECG print-outs should be identified with patient number, year of birth and gender, as well as with the date and time of recording. All print-outs should be assessed, dated and signed by the Investigator and stored in the patient's record.

8.5.2.6 Clinical laboratory evaluation

Safety laboratory assessments will be performed at each study visit except at Visit 5-6, Visit 28-29 and during End of Treatment. Pregnancy test will be performed, if applicable, during Screening Period, at Visit 11, at Visit 27, at Visits 35-38 and at the End of Study Visit. In addition, female patients of childbearing potential are required to undergo a monthly pregnancy test until 6 months from the last study drug administration. Urinalysis will be assessed prior to and at the end of the first "ramp-up" administration visit (Visit 1/Day 1, Visit 2/Day 2 and Visit 3/Day 3). The assessment of anti-HIV antibodies, anti-HBcAg antibodies, HBV-DNA and HCV-RNA will be performed ONLY during the Screening Period. Safety tests will be performed by the local laboratory of participating sites in order to ensure prompt patient management. For the same reason, tests for anti-HIV antibodies, anti-HBcAg antibodies, HBV-DNA and HCV-RNA will be performed by the local laboratory of participating sites according to local standard procedures. Results of laboratory tests for anti-HIV antibodies, anti-HBcAg antibodies, HBV-DNA, HCV-RNA which have been performed within 3 months prior to Screening Period in the context of the standard patient's management (either in the local lab or in a different lab, provided that they comply with local standard procedures) can be reported in the e-CRF under Screening Period procedures. In such case, there is no need to repeat the above mentioned tests. Laboratory values have to be transcribed into the e-CRF, except for the urinalysis where only the

judgment will be reported; the Sponsor will be provided by the site laboratories with the currently valid version of the respective normal ranges (any update of reference ranges needs to be notified on an ongoing basis).

The lab print-outs should be identified with the patient number. All print-outs should be dated and signed by the Investigator and stored in the patient's record. Any out of range value shall be clinically assessed by the Investigator.

The volume of blood to be drawn for each battery of safety lab tests will amount to approximately 15 mL.

The following tests will be performed:

SERUM CHEMISTRY	SERUM VIROLOGY	HAEMATOLOGY	URINALYSIS
Creatinine	Anti-HIV antibodies	Haemoglobin	pН
Uric acid	Anti-HBcAg antibodies	Haematocrit	Density
Potassium	HBV-DNA	RBC count	
Phosphorus	HCV-RNA	Platelet count	
		MCV	
Calcium		WBC count and	Nitrite
		differential (absolute and	
		%):	
DI IN/I Iroo		neutronhil	Protein
Albumin		lymphocyte	Glucose
Alkaline phosphatase		eosinophil	Ketones
Glucose		basophil	RBC
Total proteins		monocytes	WBC
Total bilirubin and Direct		11.	
bilirubin		blasts	Epithelial cells
ALT and AST			Casts
LDH			Bacteria
GGT			Yeast
INR			Crystals
Prothrombin time and/or			
prothrombin activity			
Partial thromboplastin time			
Fibrinogen			
D-aimer			
Amylase			
Chloride			
Beta-HCG (if applicable)			

Table 3: Serum, Blood and Urine Sample Analyte Listing

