who, throughout the study, experienced DLT events that clearly started during the infusion and that were characterized by increased transaminases, with or without severe coagulation derangements and multiorgan failure A panel of widely acknowledged AML experts was also called to advice on the pathophysiology of the above events as well as on the next steps for the prosecution of the clinical development of MEN1112 in AML. The experts concluded that the pathophysiology of the severe events observed so far in the above patients may involve cytokine storm and/or monocytic-macrophage activation, as well as massive lysis of target cells and that, to possibly prevent the occurrence of such events or limiting their severity, general safety measures should be applied. Based on the experience with other compounds (e.g. Blinatumomab, Venetoclax) and on the fact that the above toxicities did develop either at the first or the second dose during the first cycle of treatment, a "ramp-up" approach during Cycle 1 was concluded to be the most appropriate one. Therefore, the dose escalation will be resumed from the 1.7 mg/kg dose level (i.e. from the MTD achieved using the "one shot" schedule per Protocol V4.1), under the 3+3 design and using a "ramp-up" approach during the first two MEN1112 administrations of Cycle 1. If no DLT occurs, additional dose levels will be explored at 2.0 mg/kg, 3.0mg/kg and 5.0mg/kg.

Additional intermediate dose levels may be also explored, under a 3+3 design, upon recommendation of the iDSMB that will be appointed to guide dose escalation decisions. In addition, as the clinical data collected so far are not sufficient to adequately design a maintenance treatment phase, starting from protocol version 6.1/6.2 the study will no longer encompass a maintenance phase, which is replaced by a follow-up period for safety and efficacy assessments. To serve the best interest of the patients, for those achieving at least a partial response according to protocol-defined criteria, the Sponsor commits to consider providing MEN1112 to allow the prosecution of the infusions at the frequency recommended by the iDSMB on an individual basis and after discussion with the treating Investigator and the Medical Monitor.

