3.0 mg/kg 5.0 mg/kg	Visit 1/Day 1: 0.2 mg/kg Visit 2/Day 2: 1.0 mg/kg Visit 3/Day 3: 1.8 mg/kg Visit 3/Day 3: 0.2 mg/kg Visit 9/Day 9: 1.0 mg/kg Visit 10/Day 10: 1.8 mg/kg Visit 10/Day 10: 1.8 mg/kg Visit 1/Day 1: 0.3 mg/kg Visit 2/Day 2: 1.7 mg/kg Visit 3/Day 3: 3.0 mg/kg Visit 8/Day 8: 0.3 mg/kg Visit 9/Day 9: 1.7 mg/kg Visit 9/Day 9: 1.7 mg/kg Visit 10/Day 10:3.0 mg/kg	Visit 16/Day 22: 3.0 mg/kg Visit 20/Day 29: 3.0 mg/kg Visit 24/Day 36: 3.0 mg/kg Visit 16/Day 22: 5.0 mg/kg Visit 20/Day 29: 5.0 mg/kg Visit 24/Day 36: 5.0 mg/kg

The TMDD model simulations confirm that the simulated exposure at 24 and 48 hours with 2.0 mg/kg and 3.0 mg/kg with the new proposed schedule of administration are lower than those with 1.7 mg/kg administered with *"one-shot"* schedule.

Confidential Menarini Ricerche S.p.A. Page 67 of 132

The "*ramp-up*" schedule is expected to be safer in respect of the dosing schedule in force up to protocol version 4.1 ("*one-shot*"), which has been extensively demonstrated to be tolerable up to 1.7 mg/kg as confirmed by the data collected in the 17 patients treated so far at this dose level between the dose escalation and the cohort expansion steps of the study. Therefore, the treatment of study patients will not be staggered. The "*ramp-up*" dosing also allows to stop earlier the administration of the intended full dose in case of infusion-related symptoms and/or detection of laboratory adverse events and allows a better safety profile since lower exposure are achieved with the "*ramp-up*" schedule up to 48 hours from the start of infusion – when the majority of severe toxicities occurred during the study – compared to those achieved with 1.7 mg/kg given "*one-shot*". Eventually, the following additional safety measures are implemented in the amended ARMY-1 study:

- Prior to the MEN1112 administration at Cycle 1 (Visit 1/Day 1, Visit 8/Day 8 and Visit 12/Day 15), WBC count should be ≤ 10 x 10⁹/L; hydroxyurea can be used to achieve such count (a shift of +1 day of the "*ramp-up*" administration visit is allowed, if needed).
- Specific rules are provided in this protocol to manage the MEN1112 administration in case of severe infusion-related toxicities (see §8.4.7).

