- Blood sampling for PK (pre-infusion)
- Recording of AEs and change in concomitant medications
- TLS risk assessment (see Appendix I: TLS Manual for Investigator)
- TLS prophylaxis (see Appendix I: TLS Manual for Investigator)
- Premedication (see §8.4.2)

Study drug administration

- Study drug administration, given as a 6 h infusion with constant infusion rate
- Blood sampling for safety lab test at following time points after start of infusion: 2h, 4h, 8h, 12h.
- Vital signs every 15 minutes during the first hour of study drug administration and then at the same time points of blood sampling for safety lab test

- 12-lead ECG at the end of infusion
- Blood sampling for PK (at the end of infusion, and 6h after the end of infusion)
- Recording of AEs and change in concomitant medications

Visit 2/Day 2(one day after the completion of Visit 1) and Visit 3/Day 3 (one day after the completion of Visit 2)

Prior to study drug administration

- Physical examination, including vital signs
- PS evaluation
- 12-lead ECG
- Blood samplingfor safety lab test
- Blood sampling for PK (pre-infusion)
- Recording of AEs and change in concomitant medications
- TLS prophylaxis (see *Appendix I: TLS Manual for Investigator*)
- Premedication (see §8.4.2)

Study drug administration

- Study drug administration, given as 6h infusion with constant infusion rate
- Blood sampling for safety lab test at the following time points after start of infusion: 2h, 4h, 8h, 12h
- Vital signs every 15 minutes during the first hour of study drug administration and then at the same time points of
 - blood sampling for safety lab test
- 12-lead ECG at the end of infusion
- Urine collection at the end of infusion (ONLY at Visit 3)
- Blood sampling for PK
 at the end of infusion, 6h after the end of infusion (ONLY at Visit 2), 14h after the end of infusion (ONLY at Visit 3)
- Recording of AEs and change in concomitant medications

Visit 4/Day 4, one day after the completion of the entire first *"ramp-up"*

- Physical examination, including vital signs
- PS evaluation
- Blood sampling for safety lab test
- •
- Blood sampling for PK infusion

24h after the end of last "ramp-up" dosing

Bone marrow aspirate for morphologic assessment,

Recording of AEs and change in concomitant medications

Visit 5-6/Day 5-6, one and two days after Visit 4, respectively

- Blood sampling for PK
 (44h and 68h after the end of last "*ramp-up*" dosing infusion)

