- Recording of AEs and change in concomitant medications

Visit 8/Day 8 (five days after the completion of Visit 3), Visit 9/Day 9 (one day after the completion of Visit 8) and Visit 10/Day 10 (one day after the completion of Visit 9), second 3-day "*ramp-up*" administration

Prior to study drug administration

- Physical examination, including vital signs
- Weight measurement (ONLY at Visit 8/Day 8)
- PS evaluation
- Blood sampling for safety lab test NOTE: Check that WBC count is ≤ 10 x 10⁹/L (ONLY at Visit 8/Day 8); hydroxyurea is allowed to lower WBC count.
- Blood sampling for PK (pre-infusion)
- Recording of AEs and change in concomitant medication
- TLS prophylaxis (see Appendix I: TLS Manual for Investigator)
- Premedication (see §8.4.2)

Study drug administration

- Study drug administration, given as a 6h infusion with constant infusion rate
- Blood sampling for safety lab test at the following time points after start of infusion: 2h, 4h, 8h, 12h
- Vital signs every 15 minutes during the first hour of study drug administration, after then at the same time points of blood sampling for safety lab test
- Blood sampling for PK
 at the end of infusion)
- Recording of AEs and change in concomitant medications

Visit 11/Day 11, one day after the completion of the entire second "ramp-up"

- Physical examination, including vital signs
- PS evaluation
- Blood sampling for safety lab test including pregnancy test, if applicable
- Recording of AEs and change in concomitant medications

Visit 12/Day 15, five days after Visit 10, first "one-shot" infusion

Prior to study drug administration

- Physical examination, including vital signs
- Weight measurement
- PS evaluation
- Blood sampling for safety lab test

NOTE: Check that WBC count is $\leq 10 \ge 10^{9}$ /L; hydroysurea is allowed to lower WBC count.

- Blood sampling for PK (pre-infusion)
- Recording of AEs and change in concomitant medications
- TLS prophylaxis (see Appendix I: TLS Manual for Investigator)
- Premedication (see §8.4.2)

Study drug administration

- Study drug administration, given as a 6h infusion with constant infusion rate
- Blood sampling for safety lab test at the following time points after start of infusion: 2h, 4h, 8h, 12h
- Vital signs every 15 minutes during the first hour of study drug administration, after then at the same time points of blood sampling for safety lab test
- Blood sampling for PK (at the end of infusion)

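### No safety lab or vital sign is scheduled from Day 4 to Day 8 (about 90 h), although the patient attends Visits 5 and 6 for PK blood; adding them there is a cheap improvement

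*Combined protocol and SAP*

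**What the plan says.** Section 8.5.2.6: "Safety laboratory assessments will be performed at each study visit except at Visit 5-6, Visit 28-29 and during End of Treatment". Section 8.5.2.2 makes the same exemption: "Vital signs will be recorded throughout the study at each visit except at Visit 5-6". The flow-chart (2.2) and Appendix III agree, and Appendix III goes from Visit 4 straight to Visit 8.

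Visits 5 and 6 do take place. Section 8.5.1 schedules PK blood there, "44h and 68h after the end of last" ramp-up infusion, together with "Recording of AEs and change in concomitant medications". The next dosing visit, with labs and vital signs before the infusion, is "Visit 8/Day 8 (five days after the completion of Visit 3").

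On the timing of toxicity, section 6.3 refers to the first 48 hours from the start of infusion as the period "when the majority of severe toxicities occurred during the study". It also describes four patients who "experienced DLT events that clearly started during the infusion and that were characterized by increased transaminases", in some cases with severe coagulation derangement and multi-organ failure. It adds that "the above toxicities did develop either at the first or the second dose during the first cycle of treatment".

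**The concern.** Day 3 is the largest infusion of the first ramp-up. At the 3.0 mg/kg level it is 1.8 mg/kg, above the one-shot MTD of 1.7 mg/kg. At the 5.0 mg/kg level it is 3.0 mg/kg, above the one-shot dose of 2.5 mg/kg at which 2 of 5 patients had DLTs. The known severe toxicity shows largely in laboratory values (transaminases, coagulation). Recording adverse events at Visits 5 and 6 picks up symptoms, but not an ALT that nobody measured. In-hospital monitoring need last only 24 h after the administration visit (8.4.5), so the patient may already be at home.

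Two DLT rules in 8.5.4.1 depend on seeing the value in time:

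- A related Grade 4 non-haematological toxicity is a DLT at any duration, and 8.4.7 requires permanent discontinuation. If it is silent and back to Grade 1 or less by Day 8, it goes unseen and the patient is dosed again.
- A related Grade 3 toxicity is a DLT only if it lasts more than 7 days. If its onset is dated late, it can look too short to count.

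Under the 3+3 rule (8.4.3), a single DLT among three patients decides between escalating and adding three more.

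**Working it through.** The plan states no length for this gap, so there is no figure to reproduce. All times below are hours from the start of the Day 3 infusion.

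**Inputs**
- Infusion time: 6 h (8.5.1), or 8 h if prolonged after an interruption (8.4.7).
- Day 3 labs: 2, 4, 8 and 12 h from start (Appendix III).
- Visit 4 lab: one day after the ramp-up is complete (Appendix III). I assume it is drawn with the PK sample 24 h after the end of infusion (Appendix II).
- Visits 5 and 6: PK at 44 h and 68 h after the end of infusion (Appendix II).
- Visit 8: five days after Visit 3 (8.5.1), taken as 5 x 24 h from the Day 3 start.
- Blood per safety panel: about 15 mL (8.5.2.6).

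**Size of the gap**
- Visit 4: 6 + 24 = 30 h. Visit 8: 5 x 24 = 120 h. Gap: 120 - 30 = 90 h = 3.75 days.
- With an 8 h infusion: 120 - 32 = 88 h. With five days counted from the end of a 6 h infusion: 126 - 30 = 96 h. The permitted +1 day adds 24 h, giving 112 to 120 h.
- Attended visits inside the gap: 6 + 44 = 50 h and 6 + 68 = 74 h.

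**Day 3 share of the dose**
- 1.0/1.7 = 59%; 1.2/2.0 = 1.8/3.0 = 3.0/5.0 = 60%.

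**Grade 3 dating**
- This takes onset as the first abnormal value (the protocol does not say) and the end of the episode as known exactly.
- An onset just after 30 h passes 7 days at 30 + 168 = 198 h. Dated from 120 h, it passes 7 days at 120 + 168 = 288 h.
- A true duration of more than 7 and up to 7 + 3.75 = 10.75 days could therefore be recorded as 7 days or less.

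**Silent Grade 4 (illustration only)**
- If onset is uniform over the 90 h, an abnormality lasting D hours falls between scheduled labs with probability (90 - D)/90: 73% for 24 h, 47% for 48 h, 20% for 72 h.
- These figures are conditional on such an event starting in the gap. How often that happens is unknown.

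**With labs at Visits 5 and 6**
- The intervals become 50 - 30 = 20 h, 74 - 50 = 24 h and 120 - 74 = 46 h.
- The longest delay in this gap is 46/24 = 1.9 days, so the Grade 3 range shrinks to about 7 to 8.9 days.
- The 24 h illustration falls to (46 - 24)/90 = 24%, and the 48 h one to 0.

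**Other Cycle 1 gaps, unchanged by the fix**
- Day 11 to Day 15: 120 - 30 = 90 h from the Day 10 start.
- Day 18 to Day 22: 168 - 72 = 96 h = 4.0 days from the Day 15 start.

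**Cost**
- Cycle 1 panels: 15 + 1 + 15 + 1 + 5 + 3 = 40, or 40 x 15 = 600 mL.
- Two more: 2 x 15 = 30 mL, and 30/600 = 5%.

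**The case against.** The exemption is deliberate and is stated consistently. Days 1 to 4 already carry 5 + 5 + 5 + 1 = 16 panels. The only direct evidence on onset points to the infusion itself. To do harm, an event must cause no symptoms, be unremarkable on Day 4, arise after that, and then either recover by Day 8 or last just over 7 days. Safeguards exist: adverse event recording at Visits 5 and 6, recommended unscheduled assessments, fibrinogen monitoring, TLS marker monitoring in Appendix I, daily liver tests once a Grade 3-4 transaminase event is known, and the check before the Day 8 dose. The iDSMB sees every recorded event and can adjust escalation (8.4.3.1). All of this stands and keeps the point small. None of these safeguards, however, sets a measurement between 30 h and 120 h.

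A reader might infer three stronger things that the documents do not support:

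- *That ramp-ups are followed less closely than one-shots.* Section 8.5.1 treats the three ramp-up infusions as one administration visit. Counted that way, every administration has labs on four consecutive days: Days 1-4, 8-11, 15-18, 22-25, 29-32 and 36-39.
- *That sampling stops 18 h short of the plan's own 48 h risk period.* The subtraction 48 - 30 = 18 h requires the clock to start on Day 3. Section 6.3 counts from the start of infusion when it compares ramp-up with one-shot exposure. For the ramp-up that can be read as Day 1, in which case the 48 h end about when the Day 3 infusion begins. A Day 3 anchor is arguable because the largest fraction is given then, but it is an inference.
- *That an affected patient would skip the second ramp-up, fall below the 80% dose rule and be replaced.* Section 8.4.7 provides for interruption, completion of the residual dose, postponement or permanent discontinuation. It does not provide for omitting a ramp-up and carrying on.

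**Conclusion.** The gap is real: nominally 90 h without a scheduled safety lab or vital sign (88 to 96 h depending on how the interval is counted, up to 120 h with the one-day window), with two attended visits inside it. The consequence is limited to a symptom-free laboratory abnormality that arises after an unremarkable Day 4 panel. A Grade 4 value that recovers by Day 8 could be missed, and a Grade 3 onset could be dated up to 3.75 days late. The dating figure assumes that onset is taken as the first abnormal value.

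A reader might go on to infer that DLTs will be undercounted or the MTD set too high. The documents do not support that: they give no rate for such events, and escalation is not automatic. This is a worthwhile low-cost improvement in safety and DLT ascertainment, not the repair of an error.

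**What to change.** In the flow-chart (2.2), 8.5.1, 8.5.2.2, 8.5.2.6 and Appendix III, with the synopsis visit list matched, add the existing local safety panel and vital signs at Visits 5 and 6. Draw the panel with the scheduled PK samples. Vital signs are included because the patient may have left hospital.

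The cost is two local panels and about 30 mL of blood per patient. Cycle 1 safety-panel blood rises from about 600 to 630 mL, or 5%; PK and other blood comes on top of both figures. No visit or venepuncture is added.

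The gain is confined to this one gap, where the longest interval falls from 90 h to about 46 h. The Day 11-15 and Day 18-22 gaps contain no visit on which to add a lab. The Cycle 1 worst-case dating delay therefore stays at about 4 days, and the amendment should not claim otherwise.
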